#### 4.2.2 Secondary Endpoints

- Detailed PK characteristics of the product.
- The collection of safety information and AEs information over 540 days in participants treated with the OLANI.

#### 4.2.3 Primary Efficacy Endpoint:

• Proportion of participants who tolerate OLANI and maintain blood level of naltrexone of at least 1.33 ng/mL at all collected time points to ≥180 day time point.

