# V. PROTOCOL SUMMARY

Title:	A PILOT PHARMACOKINETIC TRIAL OF THE O'NEIL LONG ACTING NALTREXONE IMPLANT
Overview:	A Phase I/II, Single Arm, Open Label study measuring the Pharmacokinetics of the O'Neil Long Acting Naltrexone Implant (OLANI).
	This study will examine the pharmacokinetic profile of OLANI over 540 days in participants without a DSM 5 - Substance Related Disorders classification. Participants will be required to undergo a Naloxone Challenge Test (NCT) to confirm opiate naivety before administration of the study medication. All participants will be treated with a double administration of a 1.8g () OLANI in an open label manner. No randomization will occur.
Objectives:	Primary:
	To characterize the pharmacokinetic profile ( $C_{max}$ , $T_{max}$ , AUC, T>MEC, where MEC = 1.33 ng/mL NTX, Time to C 0 for naltrexone) of the OLANI (2 units).
	Primary outcomes used to determine these properties will be based on results from plasma concentration of naltrexone and $6$ - $\beta$ -naltrexol as ascertained from blood samples taken at the following time points:
	- 0, 3, 6, 12, 24, 48 hours
	
 
4, 8, 14, 21, 28, 35, 42, 49, 56, 90, 120, 150, 180, 210, 240, 270, 300, 330, 360, 390, 420, 450, 480, 510 & 540 days.
 

	Note: 1.33 ng/mL is a target MEC for this protocol. The MEC will be further developed over time.
	Secondary:
	• To characterize the safety profile (i.e. adverse events, laboratory results, wound site and inflammatory response rates) of the OLANI.
Endpoint:	Primary:
	The collection of at least 75% pharmacokinetic blood time points including 2 consecutive monthly naltrexone blood levels recorded at <0.1 ng/mL in 10 participants.
	Primary Efficacy Endpoint: Proportion of participants who tolerate OLANI and maintain blood level of naltrexone of at least 1.33 ng/mL at all collected time points to $\geq$ 180 day time point.
Population:	20 healthy participants (10 male, 10 female), aged between 18 and 55 years old, without a DSM 5 - Substance Related Disorders classification.

Phase:	I/II
Number of Sites:	One site: Substance Use Research Centre (SURC), New York State Psychiatric Institute, [name] (initial assessment, follow up to 48 hours, Final Visit or Early Termination Visit, and additional follow up visits as appropriate)
	Satellite Location 1: Columbia University Medical Center (CUMC), [name] (IP administration)

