#### **3 OBJECTIVES AND PURPOSE**

#### **3.1 PRIMARY OBJECTIVES**

To characterize the pharmacokinetic profile ( $C_{max}$ ,  $T_{max}$ , AUC, T>MEC, where MEC = 1.33 ng/mL NTX, Time to  $C_0$  for naltrexone) of the OLANI (2 units).

Primary outcomes used to determine these properties will be based on results from plasma concentration of naltrexone and 6- $\beta$ -naltrexol as ascertained from blood samples taken at the following time points:

- 0, 3, 6, 12, 24, 48 hours
- 4, 8, 14, 21, 28, 35, 42, 49, 56, 90, 120, 150, 180, 210, 240, 270, 300, 330, 360, 390, 420, 450, 480, 510 & 540 days.

Note: 1.33 ng/mL is a target MEC for this protocol. The MEC will be further developed over time.

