Participants will be instructed to attend the Clinilabs clinic to continue study procedures on an outpatient basis as per the protocol time points outlined in Table 7-1. There are allowable variations in actual day of collection as long as the variation is recorded. The following will be collected at all time points: Concomitant medical review, PK blood collection, AE monitoring, vital signs (Blood pressure, heart rate, respiratory rate, and oral body temperature) and a Wound Site/Implant Site assessment (see section 7.1.1.4).

The following will also be collected on day 28 and then monthly as outlined in Table 7-1, PHQ & BDI-II, C-SSRS, FBC, FCP, UA, Pregnancy test (initial with urine with serum testing used to confirm positive results), substance use reporting (self-report using the Quantitative Substance use Inventory) and UDS.

Note: As appropriate, participants may be seen for follow-up visits at the SURC clinic (i.e. if clinically indicated or if traveling to the Clinilabs clinic presents a hardship to a participant).

**SARS-CoV-2 Note:** This study is being conducted in New York, NY; a location heavily impacted by the COVID-19 pandemic. Therefore, for the safety of study participants, the IRB requested on 21 April 2020 that in-persons study visits be stopped and replaced with telephone or video visits. Thus, where in-person study visits are not possible, safety will be monitored remotely. This change means that for some participants, certain procedures (e.g. PK blood draws), may be missed during the time of the public health emergency. Table 7-1 has been updated to indicate which procedures will be captured by telephone/video visits and which procedures may be missed due to COVID-19. In case there are safety concerns that need in-person evaluation to determine best course of action, such as new-onset implant site-reaction or site drainage, then an in-person visit at the clinic will be conducted.

This change was implemented on 27 April 2020 and all missed visits/procedures are being tracked. In person visit will resume immediately when deemed safe and appropriate by the IRB.

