#### **10.3 ANALYSIS DATASETS**

The analysis will be performed based on Intention-to-Treat and Per-Protocol in all participants enrolled. Assessment of primary outcomes will be performed on participants who complete at least 75% of applicable time points.

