#### 10.4.7.2 Efficacy Review

An interim analysis will be carried out once at least 10 participants have completed their Day 180 PK blood time point. Participants, who submitted at least 14 of 19 valid blood samples (including the Day 180 sample) and safety data will be evaluated whether or not they met the MEC criteria (naltrexone blood level above 1.33 ng/mL). The analyzed interim data will be used in the planning and design of a bioequivalence/safety study of the OLANI against a reference extended release naltrexone product.

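### The primary efficacy endpoint tests 1.33 ng/mL only at collected draws, so missed draws can only hold or raise the success proportion, and only the interim rule requires a Day 180 sample

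*Combined protocol and SAP*

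**What the plan says.** The Protocol Summary and Section 4.2.3 define the endpoint in the same terms: the participant must tolerate the implant and "maintain blood level of naltrexone of at least 1.33 ng/mL at all collected time points to ≥180 day time point". Neither place says how a scheduled draw that was not collected is classed (failure, not evaluable or imputed), and no part of Section 10.4 does so either.

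Three other provisions bear on it:

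- **Section 10.3** sets a completeness floor: "Assessment of primary outcomes will be performed on participants who complete at least 75% of applicable time points". It does not say whether this includes the primary efficacy endpoint. The sentence before it points to a different population: "The analysis will be performed based on Intention-to-Treat and Per-Protocol in all participants enrolled". Section 10.4.2 repeats the 75% figure, but for the sample-collection endpoint.
- **Section 10.4.7.2** sets the interim rule: "Participants, who submitted at least 14 of 19 valid blood samples (including the Day 180 sample"). It applies to the interim review only.
- **Section 7.3.5** says of the COVID-19 period that "certain procedures (e.g. PK blood draws), may be missed during the time of the public health emergency". Footnote 14 of Table 7-1 ties this to the monthly follow-up visits, which start at Day 90. Section 7.3.8 also expects missed and late visits, and promises an analysis allowance for late samples without defining it.

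**The concern.** Under the endpoint as worded, failure needs an observed value below 1.33 ng/mL. A draw that was never taken cannot supply one. With the product unchanged, a worse data set therefore gives the same success proportion or a higher one.

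The draws that matter most for a claim about 180 days are the late ones. They are sparse (four monthly draws from Day 90 to Day 180), and they are the ones that remote visits can remove. This is the trial's named efficacy proportion, and its interim version is meant to inform the design of the next study. With 10 to 20 participants, reclassifying one person moves it by 1/20 = 5 to 1/10 = 10 points.

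**Working it through.** **1. Reproduce the plan's 19.** Section 3.1 lists six draws in the first 48 hours ("0, 3, 6, 12, 24, 48 hours") and then a list numbered by day: "4, 8, 14, 21, 28, 35, 42, 49, 56, 90, 120, 150, 180, 210, 240, 270, 300, 330, 360, 390, 420, 450, 480, 510 & 540". Thirteen of the day-numbered draws fall at or before Day 180, so 6 + 13 = 19, which matches Section 10.4.7.2. All 25 give 6 + 25 = 31 draws to Day 540. Section 5.1 expects the baseline level to be zero, so the 0-hour sample is left out below, leaving 18 post-dose draws to Day 180.

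**2. Direction.** Success is the product, over collected draws, of the indicator that the level is at least 1.33. Removing a factor that is 0 or 1 can leave the product unchanged or raise it from 0 to 1. It cannot lower it. No model is needed.

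**3. Final analysis under the 75% floor, if it applies.** The floor is 0.75 × 19 = 14.25, so 15 draws, or 0.75 × 31 = 23.25, so 24 draws. A participant missing Days 90, 120, 150 and 180 has:

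- 19 − 4 = 15 draws to Day 180, 15/19 = 78.9%
- 31 − 4 = 27 draws overall, 27/31 = 87.1%

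Both pass. The last level observed in the first 180 days is at Day 56.

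**4. Interim rule.** 19 − 14 = 5 draws may be missing, but not Day 180. Missing Days 90, 120 and 150 leaves 16 of 19, which passes. The gap is 180 − 56 = 124 days, or 124/180 = 69% of the period.

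**5. Illustration, steady decline.** The documents give neither a missing-draw rate nor a decline time, so both are assumed. The time at which the level falls below 1.33 for good is lognormal with CV 30%, and each of the 18 post-dose draws is missed at random. Success proportion under the 'collected' wording:

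| Assumed median time | No draws missed | 10% missed | 25% missed | 40% missed |
|---|---|---|---|---|
| 150 days | 0.265 | 0.291 | 0.344 | 0.416 |
| 180 days | 0.499 | 0.524 | 0.571 | 0.627 |
| 210 days | 0.701 | 0.719 | 0.750 | 0.787 |

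The rise runs from 0.719 − 0.701 = 0.018 to 0.416 − 0.265 = 0.151. In the row with median 180 days and 25% missed, a 14-of-19 floor alone gives 0.554, and the floor plus an observed Day 180 sample gives 0.501 against a true 0.499. Under steady decline the inflation comes from not requiring Day 180.

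**6. Illustration, transient dips.** Suppose there is one draw below 1.33 among the 18, and five are missed at random. It is hidden with probability 5/18 = 28%. If Day 180 must be present and the dip is elsewhere, the figure is 5/17 = 29%. Requiring Day 180 does not help here; only a minimum on the other draws does.

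**The case against.** The strongest reply has four parts.

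- **The plan is silent; it does not rule that missing means maintained.** A reader might infer that missing samples are formally treated as at or above 1.33. No section says so, and the reference to Day 180 in Section 4.2.3 can be read as requiring observation to that day. That stands as far as it goes. But only the interim section states the requirement, and the rule as worded still gives a missed draw no way to count against success.
- **The interim is the better-protected analysis.** A reader might infer a gain of 9 to 18 points at the interim by comparing nine draws with four: 0.98^9 = 0.834 against 0.98^4 = 0.922, or 0.95^9 = 0.630 against 0.95^4 = 0.815. The documents do not support that as a size. The 2% and 5% chances of a low draw are assumed, independence between draws is doubtful for a slow-release implant, and every participant would have to miss the maximum of five draws, all between Day 49 and Day 150.
- **The COVID-19 provision is narrower than it looks.** A reader might infer a gap of 180 − 42 = 138 days. The interim rule permits it, but it needs Days 49 and 56 missing too, and footnote 14 is not attached to those visits. Remote visits alone give at most 124 days if Day 180 is drawn. Timing may also limit the effect: a 22-month study with 540-day participation (about 18 months) implies roughly 4 months of enrolment, safety laboratory results were in hand by version 0.11 (June 2019), and remote visits began on 27 April 2020. If that pace held, most draws to Day 180 came before the pause. Enrolment dates are not given, so this cannot be settled.
- **The stakes are modest.** This is a single-arm pilot with no hypothesis test (Section 10.2), the primary endpoint is sample collection, and 1.33 is a provisional target. Individual data are tabulated and profiles plotted (Sections 10.4.3 and 10.4.10), so gaps would be visible. That stands and lowers the severity. It does not correct the proportion itself.

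**Conclusion.** The point holds as a property of the endpoint's wording: missed draws can only keep or raise the success proportion, and no stated safeguard closes this for the final analysis. The 75% floor may not apply. If it does, it passes a participant with no draw from Day 90 to Day 180. The interim rule fixes Day 180 but leaves Days 90, 120 and 150 free to be missing together.

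The size is unknown. It is close to zero if levels fall steadily and Day 180 is observed. If Day 180 may be missing, the steady-decline illustration gives about 2 to 15 points, which rests wholly on assumed decline times, 10% to 40% of draws missed, and missingness at random. Transient dips could be hidden under either analysis. It should be corrected, but it does not undermine the pilot.

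**What to change.** Amend Sections 4.2.3 (and the matching Protocol Summary text), 10.3 and 10.4.7.2 as follows.

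1. Keep the condition that every collected post-dose sample within a stated assessment period is at least 1.33 ng/mL, so that an observed low value at any visit still means failure. State where the period ends and that the pre-dose sample is excluded.
2. In both the interim and the final analysis, also require an observed Day 180 sample and no more than one missing draw among Days 90, 120 and 150. If Day 56 is drawn, the longest gap falls from 124 days to 120 − 56 = 64 days.
3. Class participants who have no observed value below 1.33 but lack these samples as 'not shown to maintain'. Keep them in the denominator, and report the proportion with them counted as failures and again as successes, as lower and upper bounds. Either one alone would be biased.
4. Say in Section 10.3 whether the 75% floor applies to this endpoint.
5. Report the proportion at or above 1.33 ng/mL at each visit, with its denominator.

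Cost: a protocol wording amendment, since Section 4.2.3 is a protocol endpoint, made in an open-label trial already under way. It should therefore be dated and justified before the proportion is computed. The reported proportion will be somewhat lower, or its bounds wider, where draws were missed. No new data are needed.

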#### 4.2.4 Secondary Efficacy Endpoints:

- Mean Cmax, Tmax, AUC for naltrexone blood level
- Mean T>MEC for naltrexone, where MEC = 1.33 ng/mL
- Mean Cmax, Tmax, AUC for 6β-naltrexol blood level
- Frequency of AEs and SAEs

#### 4.2.5 Exploratory Efficacy Endpoints:

• Use of drugs (opioids, cocaine, marijuana) and alcohol, as reported by participants and detected using urine drug screen (UDS).

# 5 STUDY ENROLMENT AND WITHDRAWAL

#### 5.1 PARTICIPANT INCLUSION CRITERIA

Healthy participants without a DSM 5 - Substance Related Disorders classification will be recruited for this study. Participants will be assessed for their general health and mental health status.

Participants will be required to undergo a NCT to confirm opiate naivety before administration of the study medication. Participants will be required to not have had a naltrexone implant or any other extended release naltrexone preparation administered within the last year. A naltrexone blood sample will be taken at baseline to confirm zero naltrexone levels for data analysis.

To qualify for the study participation, participants must also be:

- 1. Men or women between the ages of 18 and 55 years old (inclusive)
- 2. Without DSM 5 Substance Related Disorders classification; in sustained remission is not exclusionary
- 3. Able and willing to comply with the requirements of the protocol
- 4. Able and willing to provide written informed consent
- 5. Willing to undergo a minor surgical procedure under local anesthetic to allow for investigational drug administration in the subcutaneous tissue
- 6. Have an initial weight between 45.3 and 81.6 kilograms (inclusive) or have a BMI inclusive of 18.5 to 30.0

#### 5.2 PARTICIPANT EXCLUSION CRITERIA

An individual who meets any of the following criteria will be excluded from participation in this study:

- 1. Positive UDS at screening for illicit substances.
- 2. Is currently on naltrexone medication.
- 3. Has had a naltrexone implant in the past 24 months.
- 4. Has received treatment with an extended naltrexone product (e.g. Vivitrol) in the past 12 months.
- 5. Has a condition which requires treatment with opioid based medication.
- 6. Has a known hypersensitivity to naltrexone.
- 7. Has a known hypersensitivity to poly-lactic based materials e.g. biodegradable sutures, surgical implants or previous biodegradable implants.
- 8. Has a known hypersensitivity to local anesthesia.
- 9. Is prone to skin rashes, irritation or has a skin condition such as recurrent eczema that is likely to impact the implant site area, or as determined by the evaluating physician.
- 10. Demonstrates any abnormal skin tissue in the proposed implantation area.

- 11. Is pregnant or planning to be. Women need to have negative blood pregnancy test at screening. Women need to agree to practice dual contraceptives.
- 12. Participant is breastfeeding or planning to be.
- 13. Has a current significant neurological (including cognitive and psychiatric disorders), hepatic, renal, endocrine, cardiovascular, gastrointestinal, pulmonary, hematological or metabolic disease unless currently controlled and stable with protocol-allowed medication 30 days prior to proposed investigational product administration.
- 14. Any clinically important abnormal finding as determined by medical history, physical examination, ECG or clinical laboratory tests.
- 15. Any additional condition(s) that in the investigator's opinion would prohibit the participant from completing the study or would not be in the best interest of the participant.
- 16. ALT or AST > 3 times the upper end of the laboratory normal range.
- 17. Any methadone use 14 days prior to screening, and up to Study Day 0.
- Current DSM 5 diagnosis of schizophrenia, bipolar, anxiety, or depressive disorder, confirmed by MINI assessment, or currently treated with medications for anxiety or depression. Past history (in remission DSM 5 classification) of anxiety or depression is not exclusionary.
- 19. Any elevated risk for suicide measured using the Columbia Suicide Severity Rating Scale, endorsing any of the items in the past month (C-SSRS, Lifetime)
- 20. Is participating or intending to participate in any other clinical trial during the duration of this study.

#### 5.3 STRATEGIES FOR RECRUITMENT AND RETENTION

#### 5.3.1 Target Sample Size:

A total of 20 participants (10 females and 10 males) will be recruited. We expect that 10 of the 20 participants will complete the study (50%), which is providing at least 75% valid pharmacokinetic blood samples including 2 monthly naltrexone blood levels recorded at <0.1 ng/mL.

#### 5.3.2 Recruitment

After reading the study consent participants will be seen by a research psychiatrist or psychologist for a screening evaluation and mental status examination as part of routine admission procedures at SURC. Final informed consent for the study will be obtained after full psychiatric and medical workup is complete. The research staff knows the protocol well and is able to explain study to the participant. Procedures for training staff physicians in each protocol and consent form include initial presentations by the Principal Investigator (PI) at weekly staff meetings, and weekly discussion of inclusion/exclusion criteria and study eligibility for each screening participant.

The use of the Contract Research Organization (CRO) Clinilabs, will also allow access to their participant database where the majority of healthy volunteers are expected to be recruited.

# 5.3.3 Retention

All participants will be reimbursed as per section 7.9 for each clinic visit to compensate them for the time spent doing research assessments as well as the cost of transportation. We will maintain a close phone contact with participants to confirm each visit, and to reschedule in case of the missed visit.

#### 5.4 PARTICIPANT WITHDRAWAL OR TERMINATION

#### 5.4.1 Reasons for Withdrawal or Termination

- A participant may withdraw from the study at any time or for any reason without being obliged to divulge their reason for doing so to the investigators or clinic staff.
- A participant may be withdrawn from the study if there are unacceptable AEs, laboratory abnormality or any other medical condition or situation including distress due to effects of any study procedure or medication.
- A participant may be withdrawn from the study if in the opinion of the treating clinician the participant's interests are best served by withdrawing from the study.
- A participant may be withdrawn from the study if the participant meets an exclusion criterion (either newly developed or not previously recognized) that precludes further study participation.
- Participant will be withdrawn from the study if they fail the naloxone challenge test.

#### 5.4.2 Handling of Participant Withdrawals or Termination

Participants, who do not receive the study medication (OLANI), for any reason, are not considered treatment failures. A participant may be discontinued from the study at any time if the participant, investigator, or sponsor determines that it is not in the best interest of the participant to continue participation. Reasons for discontinuation may include:

- Adverse event
- Withdrawal of participant
- Lost to follow-up
- Study terminated by investigator
- Pregnancy
- Clinical worsening
- Other
- Screen Failure

#### 5.4.2.1 Participant Monitoring and Removal from Study

Medical staff will assess and communicate with the study PI the appropriateness for continuation in the research study on a continuous basis and will remove from the trial participants with significant clinical deterioration or noncompliance of a type which could be dangerous. Criteria for removal from the study will include:

1. Clinical deterioration which cannot be managed safely in the context of outpatient treatment. This would include a participant who becomes suicidal, or a participant

who goes on severe drug binges (including non-opiate drugs), endangering him/herself.

- 2. Elevation of liver enzymes > 3 times normal. The PI or a study physician is available 24 hours/day by phone and/or beeper in case of emergency.
- 3. Participant becomes pregnant. In case of incidental pregnancy, the participant will remain in the study and will be followed until the resolution of pregnancy. To reduce unnecessary procedures, we will stop PK blood draws, unless clinically indicated, however the safety monitoring will continue. In addition, we will collect safety information related to the pregnancy and birth outcomes. After finding an incidental pregnancy the removal of the implant will be offered to the participant and the participant will decide how best to proceed in consultation with her obstetrician. The decision regarding the pregnancy will affect the decision whether or not to remove the implant at any point during the pregnancy. The risk of anesthesia differs during different times during pregnancy, however the risks of anesthesia and the risks of removal are both minimal.

If a participant becomes pregnant, PK labs will no longer be collected, but the participant will be followed for safety monitoring for the remainder of the study.

For those who withdraw from the study, (data collection and / or treatment) there are two main options:

- **Option 1:** Withdrawing from data collection and no further contact with study personnel. This carries the least amount of risk, with option 2 carrying some risk.
- **Option 2:** Removal of the study medication via surgical procedure. Whilst removal of the study medication is straightforward in the early stages (up to about 10 days), removal after this becomes more complex as the OLANI biodegrades. Later procedures require a general anesthetic (with access to OR facilities) and may result in a large scar certainly larger than not removing the implant but the extent depends on the amount of tissue to be excised. The risks associated with general anesthetic vary between people, but about 20% of those receiving general anesthesia have minor AEs and 0.2% have major AEs including death. If removal of the implant is the only acceptable option to the participant, this will be arranged through either Columbia University Medical Center or another local hospital.

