- 6. Naltrexone has been associated with reversible hepatocellular injury indicated by elevated liver enzymes when administered at doses substantially greater than the doses expected in this study. When used in the lower dose range in opiate dependent patients, this risk is remote. Naltrexone is therefore contraindicated in participants with acute hepatitis or liver failure, and such participants are excluded from the study. Participants with hepatic enzyme levels greater than three times the upper limit of normal are excluded. Implantable naltrexone achieves lower blood levels than oral naltrexone initially, and blood level should remain lower throughout treatment period than levels associated with hepatitis. If naltrexone induced hepatitis were to occur in the setting of long-acting preparation, where the naltrexone would be only very slowly eliminated, this would prolong exposure to the offending agent. However, the experience with injectable and implantable naltrexone also suggests it is safe. In studies with injectable naltrexone several participants experienced elevation in liver enzymes, which were determined to be related to hepatitis C. Several recent reports with injectable naltrexone showed that it poses significantly lower risk of hepatotoxicity than previously suspected, even among alcohol and opioid-dependent persons including those with HCV and/or HIV infection. In July of 2013, the Boxed Warning on the hepatotoxicity was removed from the Vivitrol Package Insert."
- 7. Naloxone injection may cause withdrawal symptoms such as nausea, vomiting, diarrhea, stomach pain, fever, sweating, body aches, weakness, running nose, goosebumps, shivering, increased heart rate, and anxiety.

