## 8 ASSESSMENT OF SAFETY

#### 8.1 SPECIFICATION OF SAFETY PARAMETERS

Safety will be assessed on the basis of:

- the incidence of death
- the incidence of SAEs
- the incidence AEs leading to discontinuation
- the incidence common AEs
- the incidence complications of insertion
- the incidence implantation site reactions
- laboratory abnormalities indicating hepatic problems (absolute values and changes over time)

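### Removal from the study under Section 5.4.2.1 ends serial PK sampling, the monthly laboratory visits and, after 7 or 30 days, new-event capture while the implants may still be releasing naltrexone; liver follow-up continues but becomes event-driven

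*Combined protocol and SAP*

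**What the plan says.** **Removal.** In Section 5.4.2.1 the words "Criteria for removal from the study will include" introduce three items: clinical deterioration that is unsafe to manage as an outpatient, "Elevation of liver enzymes > 3 times normal", and pregnancy. What is described is removal from the study. There is no later dose to withhold, because both units are implanted in one procedure (Sections 6.1.5 and 7.1.1.3).

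**Pregnancy.** The third item then says that "the participant will remain in the study and will be followed until the resolution of pregnancy". It stops PK draws with an exception for clinical need. A following paragraph stops them with no exception.

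**Withdrawal options.** Option 1 in the same section is "Withdrawing from data collection and no further contact with study personnel". Option 2 is surgical removal of the implants, of which the section says that, after about 10 days, "removal after this becomes more complex as the OLANI biodegrades". The liver criterion does not itself call for Option 2. Section 2.3.1, on hepatitis under a long-acting preparation "where the naltrexone would be only very slowly eliminated, this would prolong exposure to the offending agent", accepts that exposure would go on.

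**After leaving.**
- Section 7.3.7 requires an early termination visit. Table 7-1 marks one PK sample and one set of safety laboratory tests there.
- Sections 7.3.7 and 7.3.10 make a 30-day in-clinic visit mandatory for an AE that needs laboratory testing. The AE follow-up column of Table 7-1 has laboratory tests but no PK.
- Section 7.3.9 provides PK follow-up visits only after Day 540.
- Section 8.3 follows ongoing AEs to resolution, stability or loss to follow-up. New events are recorded only if they start within 7 days (non-serious) or 30 days (serious) of the last day of participation.

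**The concern.** With a daily oral drug, leaving the study usually means leaving the treatment. Here the two come apart, and the plan does not say what happens to data collection in the gap. A participant with a raised liver enzyme may go on being exposed for months with no serial concentrations to set against the laboratory course, and a new non-serious event starting on day 8 after leaving would not be recorded.

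The missing data would be caused by the safety outcome. Section 8.1 names liver laboratory abnormalities as a safety parameter, as levels and as trends, and Section 4.2.2 makes safety information over 540 days a secondary endpoint. With 20 enrolled and 10 expected to complete, one participant is a visible share of the data. The interim results also feed the design of the next study (Section 10.4.7.2).

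**Working it through.** **The plan's own figure.** Section 5.3.1 enrols 20 to obtain 10 completers at 50% completion: 10 / (1 − 0.50) = 20. This reproduces and is not in dispute.

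**Step 1: count the schedule.**
- PK points (Section 3.1): 6 from 0 to 48 hours, 9 from Day 4 to Day 56, 16 from Day 90 to Day 540; 6 + 9 + 16 = 31.
- PK points to Day 180: 6 + 9 + 4 = 19, which agrees with the 19 in Section 10.4.7.2.
- On-study safety laboratory visits (Table 7-1): Days 28 and 56 plus 16 monthly visits = 18.
- Not counted: the Final Visit, which also marks PK and laboratory tests, and any PK follow-up after Day 540. Section 7.2.3 allows for 32 PK draws; I use the 31 listed time points.

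**Step 2: what removal forfeits.** The early termination visit returns one PK sample and one laboratory set. Where the mandatory 30-day visit applies, it returns at least one more laboratory set and no PK.

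| Removed after | PK points forfeited | PK net of early termination | Laboratory visits forfeited | Laboratory net of both visits |
|---|---|---|---|---|
| Day 56 | 31 − 15 = 16 (51.6%) | 15 | 16 of 18 | 16 − 2 = 14 or fewer |
| Day 90 | 31 − 16 = 15 | 14 | 15 of 18 | 13 or fewer |
| Day 180 | 31 − 19 = 12 | 11 | 12 of 18 | 10 or fewer |

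These are upper limits on the listed schedule. Section 7.2.3 ends a participant's sampling after two consecutive monthly levels below 0.1 ng/mL and describes Day 540 as the worst case.

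**Step 3: effect on the PK analysis sets.**
- Section 10.4.2 analyses only participants with at least 75% valid samples and two consecutive monthly levels below 0.1 ng/mL. Anyone removed before two such levels is outside this set, whatever denominator the 75% uses.
- If the denominator is all 31 points, 0.75 × 31 = 23.25, so 24 samples are needed. With perfect attendance the 24th falls at Day 330 (15 to Day 56 plus 9 monthly), or at Day 300 plus the early termination sample (23 + 1). Section 10.3 refers to applicable time points, so the denominator may be smaller and this limit may not bind.
- The interim review (Section 10.4.7.2) needs 14 of 19 samples including Day 180. A participant removed before Day 180 is not evaluated there.

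**Step 4: how many participants.** The documents give no removal rate. Purely as an assumption, let each of the 20 be removed independently with probability q. The expected number is 20q, and the chance of at least one is 1 − (1 − q)^20.

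| Assumed q | Expected | At least one |
|---|---|---|
| 5% | 1 | 0.64 |
| 10% | 2 | 0.88 |
| 15% | 3 | 0.96 |

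If q is near zero, nobody is affected.

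**The case against.** **A reader might infer that liver data stop on removal.** They do not. The early termination laboratory tests, the mandatory 30-day visit and follow-up of the AE under Section 8.3 apply to exactly these participants. Section 8.3 also lets the follow-up period be extended on a schedule agreed with the sponsor, and unscheduled visits can include PK and laboratory tests at a physician's discretion. This objection stands in full for the liver finding. It does not restore a PK series, the monthly laboratory visits, or capture of new events beyond 7 or 30 days.

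**A reader might infer that the safety results are shown to be biased, or rest on completers.** The documents do not support that. Section 10.3 includes an intention-to-treat analysis of all enrolled, Section 10.4.4 counts AEs and out-of-range values for the whole group, and Section 10.4.10 tabulates individual data. The value that triggers removal will be on record. The completer restriction applies to PK and arises from the rule in Section 10.4.2, which would operate even if this point were fixed.

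**A reader might infer that every listed criterion leads to exit with continued exposure.** Pregnancy keeps the participant in the study with safety monitoring, and implant removal is available to those who leave. Section 5.4.1 also says that a laboratory abnormality may, not must, lead to withdrawal. Continued release after removal is therefore possible rather than certain.

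**The problem may never arise.** ALT or AST above 3 times the upper normal limit is an exclusion at entry, and Section 2.3.1 regards hepatic risk at lower doses as remote. The study is a descriptive pilot with no hypothesis. This is fair and limits the weight of the point.

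**Continued outpatient visits do not suit everyone.** For a participant removed because outpatient care is unsafe, research visits may not be feasible. The change has to allow for this.

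**Conclusion.** The point holds as a gap in data collection. As written, a participant who meets the liver criterion leaves the PK and monthly laboratory schedule because of a safety outcome, while the implants, unless removed, may still be releasing drug. The largest loss in the examples is 16 of 31 PK points (15 net) and 16 of 18 laboratory visits (14 or fewer net), for removal after Day 56. The size depends on when removal occurs, on how long naltrexone stays at or above 0.1 ng/mL, and on the implants staying in place. How many people it touches is unknown and may be none.

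Separately, three pairs of statements conflict and must be reconciled whatever is decided on data collection:
- pregnancy as a ground for removal against "In case of incidental pregnancy, the participant will remain in the study and will be followed until the resolution of pregnancy";
- PK draws in pregnancy stopped with an exception against stopped without one;
- Option 1, with no further contact, against the required early termination visit (Section 7.3.7) and AE follow-up (Section 8.3).

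This is a cheap improvement and does not call the study's design into question. Nothing here bears on whether the clinical thresholds, or the handling of the implants, are right.

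**What to change.** Add to Section 5.4.2.1 that, for a participant who still consents, has implants in place and can feasibly attend, meeting a listed criterion does not by itself end the PK and safety data collection already scheduled in Table 7-1. State that recording of new AEs continues for as long as those visits do, and align the 7-day and 30-day windows in Section 8.3 with this. For each criterion, say which collections continue; PK in pregnancy follows whatever the reconciled pregnancy text says. Limit Option 1 to participants who decline contact, or otherwise square it with Sections 7.3.7 and 8.3.

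The cost is amendment wording, with IRB review. The visits are already in the schedule, so the downside is continued attendance, blood draws and visit payments (Section 7.9) for what is likely to be a few participants. The clinical criteria are left as they are.
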